#### **6.5.9 Study completion and post-study treatment**

As study completion CRF page should be completed at Month 24. The investigator/the study team also will provide follow-up medical care for all patients who are prematurely withdrawn from the study, or will refer them for appropriate ongoing care. No drug will be provided after study completion at Month 24.

#### **6.5.10 Early study termination**

The study can be terminated at any time for any reason by the investigator. Should this be necessary, the patient should be contacted and seen as soon as possible and treated as described in Section 7 for a prematurely withdrawn patient. The investigator may be informed of additional procedures to be followed in order to assure that adequate consideration is given to the protection of the patient's interests. The investigator will be responsible for informing IRB of the early termination of the trial.

## 7 Visit schedule and assessments

Table 7-1 lists all of the assessments and indicates with an “x” the visits when they are performed.

Patients should be encouraged to attend all visits on the designated day. However visit windows will be allowed of  $\pm$  1 day for Days 5 and 7,  $\pm$  3 days for Days 14, 21, and 28 visits,  $\pm$  1 week for Months 2 – 12 visits, and  $\pm$  2 weeks for Months 15 – 24 visits.

Patients who discontinue study drug before completing the study, and those who prematurely withdraw from the study for any reason, should be scheduled for a visit as soon as possible, at which time all of the assessments listed for the final visit will be performed.

Patients who discontinue study drug should also return for the assessments indicated in Table 7-1, including a blood sample for serum creatinine. If they refuse to return for these assessments or are unable to do so, every effort should be made to contact them or a knowledgeable informant by telephone when they refuse to return, and at 6, 12, and 24 months to determine the information on survival status, graft loss/re-transplant, rejection episodes, malignancies, opportunistic infections and immunosuppressive therapies. Since patients will be followed even after discontinuation of study medication, the Study Completion CRF page should only be completed at Month 24 or earlier if the patient can no longer be followed, e.g. death, lost to follow-up, or withdrawal of consent.

All patients will be contacted 30 days after the last dose of study medication regarding Serious Adverse Event information. Graft loss, death and malignancy are considered to be SAEs and should be entered on a SAE form and reported to the relevant regulatory authorities during the follow-up period (beyond 30 days after the last dose). Other Serious Adverse Events that are related to study medication as assessed by the investigator should also be entered on a SAE form and reported to the relevant regulatory authorities during the follow-up period.

Patients who prematurely discontinue study medication due to death, lost to follow up or patient withdrew consent will not have any post-study follow up evaluations.

At a minimum, patients will be contacted for safety evaluations during the 30 days following the last dose of study drug or last completed visit (whichever is later), including final contact at the 30-day point. Documentation of attempts to contact the patient should be recorded in the patient record.

**Table 7-1 Evaluation schedule**

	SCR	OR	Day								Month											
	-21- 0	0	1	3	5	7	14	21	28	2	3	4	6	8	10	12	15	18	21	24		
Informed consent	X																					
Randomization	X																					
Background information	X																					
Inclusion/exclusion	X	X																				
Medical History	X	X																				
Transplant information		X																				
Viral serology	X												X		X		X	X			X	
Pregnancy test	X													X		X					X	
EKG		X																				
Vital signs		X	X	X	X	X	X	X	X	X	X	X	X	X	X	X	X	X	X	X	X	
Physical exam		X																	X			
Laboratory tests		X	X	X	X	X	X	X	X	X	X	X	X	X	X	X	X	X	X	X	X	
Renal Biopsy	X 												X 						X 			X
Study medication		X	X	X	X	X	X	X	X	X	X	X	X	X	X	X	X	X	X	X	X	
Campath dosage		X																				
Everolimus trough level					X	X	X	X	X	X	X	X	X	X	X	X	X	X	X	X	X	
Tacrolimus trough			X	X	X	X	X	X	X	X	X	X	X	X	X	X	X	X	X	X	X	
SF-36						X				X				X			X			X		X
Steroid	Per hospital protocol																					
Adverse events	As needed																					
Allograft rejection	As needed																					
Graft loss record	As needed																					
Dialysis log	As needed																					
Infection log	As needed																					
End of treatment	As needed																					
Comments	As needed																					
Follow-up record	Completed at 3, 6, 12, 18 and 24 months after the first dose of study medication for patients who prematurely discontinued study medication prior to Month 24.																					
Renal Biopsies	The study renal biopsy to be performed at 24 months. If clinically indicated biopsies were done prior to the scheduled biopsies at month 3, 12 and 24, repeat biopsy may not be performed.																					

OR: Day of transplant

Windows: Day 5, 7: ±1 day, Day 14, 21, 28: ±3 days, Month 2-12: ± 1 week, Month 15-24: ± 2 weeks

Biopsy windows: ± 4 weeks

1. Pre-transplant biopsy
2. 3-month and 1-year post-transplantation biopsies are performed as part of standard institutional protocol.

## 7.1 Information to be collected on screening failures

Patients discontinuing prior to randomization are considered screening failures. If a patient discontinues before entering the treatment period, only the Demographic information and

Screening Log entry with the primary reason for discontinuation should be completed on the CRF.

## **7.2 Patient demographics/other baseline characteristics**

After informed consent has been signed and the patient's eligibility to participate in the study has been determined, baseline patient information will be obtained, such as date of birth, age, sex, race, full relevant medical history/current medical conditions, information on renal transplantation background of recipient and donor and on transplantation procedure.

Baseline assessments will occur in the time period starting 30 days pre-transplantation and ending at the time of transplant. Results of a physical examination at a baseline, include pregnancy test (within 48 hours prior to transplantation), vital signs, blood chemistry and hematology, urinalysis, including a quantitative protein/creatinine ratio.

## **7.3 Treatment exposure and compliance**

All doses of study medication administered during the course of the study will be recorded on the appropriate Study Drug Dosage Administration CRF. Everolimus trough levels will be determined by the designated hospital laboratory.

Tacrolimus dosing will be entered on a separate TAC Dosage Administration CRF. Tacrolimus trough levels will be locally determined and recorded on the relevant CRF. Dose adjustments will be made based on local assay results.

Immunosuppressive therapies will be recorded on a separate Immunosuppressive Therapies CRF. Steroids will be recorded until steroid withdrawal occurs in accordance with MGTI's standard practice.

For all immunosuppressants, the start date, total dose, stop date and reason for administration or change are to be provided. If study drug is interrupted due to inability to tolerate oral medication and rescue therapy via an NG tube is administered the non-study drug immunosuppressive (i.e. crushed ERL suspension) should be recorded on the Immunosuppressive medications CRF. For anti-hypertensive medications,

Other drugs administered prior to and continuing at start of study medication will be entered on the 'Concomitant medications' CRF.

Immunosuppressive drugs administered prior to and continuing at start of study medication will be entered on the 'Immunosuppressive Medications' CRF.

Compliance will be assessed by the investigator and/or study personnel using pill counts (will be obtained from Investigational Drug Service pharmacy) and information provided by the patient. This information should be captured in the source document.

## **7.4 Efficacy**

### **7.4.1 Acute Rejection**

All suspected acute rejection episodes must be entered on the Kidney Allograft Rejection CRF. Suspected rejection episodes ultimately determined to be other conditions should also be entered on the Adverse Event CRF.

#### **7.4.2 Treated Biopsy Proven Acute Rejection**

Renal biopsies will be collected for all cases of suspected acute rejection. For all suspected rejection episodes, regardless of initiation of anti-rejection treatment, a graft core biopsy must be performed within 48 hours. Biopsies will be read by hospital pathologists in accordance with institutional practice. The results of the biopsy will be listed on the Kidney Allograft Biopsy CRF. The results will be used for patient management for acute rejection and for the efficacy analysis. A treated BPAR will be defined as a biopsy graded IA, IB, IIA, IIB, or III and which is treated with anti-rejection therapy.

##### **Reference to acute rejection reporting:**

Report any acute rejection episode on the Kidney Allograft Rejection CRF. No SAE form will be completed. However, if the episode is unusual in appearance or clinical course, and/or graft threatening, an Adverse Events CRF must be completed. In this particular case, a SAE form will be completed when appropriate and submitted according to procedure outline in Section 8.2.

#### **7.4.3 Kidney Biopsy**

Baseline biopsies will be obtained on all patients. 3, 12, and 24 month biopsies will be obtained for all patients. The Month 3 and Month 12 biopsies will be performed as a part of the standard of care. In addition, biopsies should also be collected for any patients with suspected viral infection, renal dysfunction, or in all cases of suspected acute rejection. Any biopsy result should be recorded on the Kidney Allograft Biopsy CRF.

#### **7.4.4 Graft Loss**

The allograft will be presumed to be lost on the day the patient starts dialysis and is not able to subsequently be removed from dialysis. If the patient undergoes a graft nephrectomy, then the day of nephrectomy is the day of graft loss. This will be reported on the premature discontinuation of study medication CRF, if medication is discontinued prematurely. The reason for graft loss will be recorded on the Graft Loss CRF. If graft loss occurs after the patient has discontinued study medication, the appropriate Follow-Up CRF should be completed. Graft loss is considered a Serious Adverse Event and should be reported on the Serious Adverse Event CRF and the SAE form must be reported to the relevant regulatory authorities within 24 hours.

#### **7.4.5 Death**

In the event of patient death, an SAE form should be completed and reported to the relevant regulatory authorities within 24 hours. The events leading to the death should be entered on the Adverse Event CRF and the death should be indicated on the premature discontinuation of study medication CRF (if death occurs while on treatment) and the Study Completion CRF.

#### **7.4.6 Renal function**

Renal function will be assessed by measuring serum creatinine, by calculated GFR using the MDRD formula, and proteinuria as determined by a spot urine protein/creatinine ratio.

#### **7.4.7 Premature study treatment discontinuation**

This will be captured on the Premature Discontinuation of Treatment CRF. Dates and reasons must be provided.

#### **7.4.8 Premature study discontinuation**

This will be captured on the Study Completion CRF. Reason must be provided.

#### **7.4.9 Appropriateness of efficacy measurements**

The efficacy variables selected are standard for this indication/patient population.

### **7.5 Safety**

#### **7.5.1 Physical examination**

A through physical examination will be performed during the baseline period and at the Month 12 and 24 visits.

Information for all physical examinations must be included in the source documentation. Significant findings that are present prior to the start of study drug must be included in the Relevant Medical History/Current Medical Conditions screen on the patient's CRF. Significant findings made after the start of study drug which meet the definition of an Adverse Event must be recorded on the Adverse Event screen of the patient's CRF.

#### **7.5.2 Vital signs / Weight**

Vital signs (radial pulse rate, blood pressure and weight (to the nearest 0.1 kilogram [kg] in indoor clothing) will be recorded at baseline, prior to the first morning administration of study medication, and at each subsequent visit. Systolic and diastolic blood pressure will be measured in accordance with MGTI's standard practice. In case the cuff sizes available are not large enough for the patient's arm circumference, a sphygmomanometer with an appropriately sized cuff may be used.

#### **7.5.3 Adverse events**

An adverse event is the appearance or worsening of any undesirable sign, symptom, or medical condition occurring after starting the study drug even if the event is not considered to be related to study drug. Medical conditions/diseases present before starting study drug are only considered adverse events if they worsen after starting study drug. The occurrence of adverse events should be sought by non-directive questioning of the patient at each visit during the study (See Section 8.1)

#### **7.5.4 Infections**

Infections should be recorded with the start and end date, type of infection, and medications used on infection log CRF. If medications are used to treat the infection, the name of the medication must be entered on the Concomitant Medications CRF. If the patient is hospitalized, an SAE form must be reported.

### **7.5.5 Major Adverse Cardiac Events**

Major Adverse Cardiac Events will be considered an SAE and will be entered in the adverse events CRF. These include acute myocardial infarction, congestive heart failure, percutaneous coronary intervention (PCI), automatic implanted cardiac defibrillator (AICD), coronary artery bypass graft surgery (CABG), cerebral vascular accident, and peripheral vascular disease

### **7.5.6 Laboratory evaluations**

All laboratory tests will be done at the hospital affiliated laboratory. Laboratory samples should be drawn prior to administration of the morning dose of both TAC and study medication. All samples will be drawn with the patient in the fasting state (more than eight hours after the last meal) if possible. Non-fasting blood samples will be clearly identified.

Therapeutic drug monitoring (TDM) will be mandatory throughout the study. The transplant team will be alerted when ERL trough levels are < 3 ng/mL or > 8 ng/mL to adjust the dose of ERL. All ERL dose adjustments will be made based on these results.

Blood samples for TAC trough levels from the hospital affiliated laboratory will be used to obtain tacrolimus trough levels. Adjustments should be made for TAC using the trough levels from the laboratory.

Extreme values will be reported to the investigator and/or the study team for immediate action as per standard of care. The Investigator is asked to comment on these abnormalities if they are clinically significant in the CRF.

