#### **Everolimus treatment arm 1:**

Therapeutic drug monitoring of everolimus and tacrolimus is mandatory throughout the study. From Day 5 on, the everolimus 0.75 mg BID dose will be increased if the trough level is < 3 ng/mL, or reduced if the trough level is > 8 ng/mL. Tacrolimus will be initiated at 0.1 mg/kg/day and adjusted according to our standard practice to achieve target trough levels. From Day 3 on, a whole blood trough concentration will be targeted for 4 to 7 ng/mL. From Month 3, the target tacrolimus trough level will be 2 ng/mL to 5 ng/mL.

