#### **4 Study Design**

This is a 24 month, Single Center, Open-Label, Randomized, Parallel assignment, non-inferiority pilot study of safety and efficacy, comparing Everolimus with low-dose Tacrolimus (2 arms; 1 arm will involve a conversion to MMF/MPA at month 3) and the standard of care (with standard dose Tacrolimus and MMF/MPA) in recipients of DCD and elevated KDPI kidneys. For this study, either MMF 1,000 mg BID or MPA 720 mg BID will be allowed since MMF and MPA are considered to be therapeutically equivalent.

All study patients must give a signed informed consent voluntarily prior to any study-related activities. Once a signed consent is obtained, baseline assessment including laboratory testing will take place to determine patient's eligibility to participate in the study. Baseline assessments will occur in the time period starting 3 weeks pre-transplantation and ending at the time of transplantation. Eligible patients will receive Campath or Simulect as an induction therapy according to the institutional practice.

Randomization will occur within 24-hour of transplantation. Fifty patients who meet the inclusion/exclusion criteria will be randomized to receive their first dose of study drug (0.75 mg Everolimus (2 arms) or 1,000/720 mg MMF/MPA) within 24 hours of transplantation (Figure 4-1). The first dose of Tacrolimus will be given to all study participants according to our standard practice. Patients will be assigned to either continuation on low-dose Tacrolimus (Arm 1), to conversion from low-dose Tacrolimus to Mycophenolate at month 3 (Arm 2), or to standard therapy with Tacrolimus and Mycophenolate (Arm 3).

Everolimus and Tacrolimus levels will be monitored throughout the study, and respective doses will be adjusted according to the desired trough levels. Patients will be started on 0.75mg BID. Everolimus will be dosed to target trough levels of 3 to 8 ng/ml, starting on Day 7.

Earlier increase in Everolimus level may decrease Tacrolimus exposure, which may lead to under-immunosuppression; increasing the risk of acute rejection (16). Therefore, Day 7 $\pm$ 1 was chosen to initiate the first dose adjustment for Everolimus after careful consideration of the half-life of this drug and turnaround time of the trough level availability. The target Everolimus trough level was determined based on the Novartis B201 and B251 studies (17).

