For Arms 1 and 2, the initial Tacrolimus dose of 0.03 mg/kg (based on ideal body weight) will be given within 24 hours of transplant. Subsequently, the target Tacrolimus trough levels will be 4 to 7 ng/ml from Day 1 to Month 3, and 2 to 5 ng/ml from Month 3 until study completion. For Arm 3, the initial dosing and adjustment will follow the institutional practice.

Patients on Arm 2 will be converted between weeks 12 and 14, after the protocol biopsy. Conversion of Tacrolimus to MMF/MPA (arm 2) will be done abruptly. On the day of conversion, MMF/MPA 1,000/720 mg will be given twice a day while no Tacrolimus will be given. In other words, there is no overlapping of Tacrolimus and MMF/MPA dosing.

For Arm 2 (after Month 3) and arm 3, MMF/MPA will be initiated at 1,000/720 mg and administered according to our standard practice in corresponding arms. Adjustment of doses may occur due to side effects, and in such cases, adjustment will follow the institutional standard practice.

All groups will be treated with corticosteroids, and prednisone will be tapered off or withdrawn according to standard practice.

[figure not shown]
For patients experiencing delayed graft function (DGF), Tacrolimus can be held up to 14 days. If this period is more than 14 consecutive days or more than two episodes of 7 days or longer, study drug discontinuation will be discussed among the study team including nephrologists. In all suspected rejection episodes, biopsy will be performed, and all patients will be treated as per our standard practice based on biopsy findings.

For patients on Arm 1 and 2 experiencing severe side effects such as complications due to delayed wound healing and mouth sores, Everolimus can be held up to 14 days. Patients who will require a prolonged discontinuation of Everolimus longer than 14 days will be withdrawn, and will be monitored as a regular follow-up until 1 month after the discontinuation. Then, patients will be monitored at a reduced follow-up schedule (Table 1).

During the 24 month study period, patients will be monitored according to the study visit schedule as listed in Table 1. The assessment to address the primary objective will be performed at month 6, 12, and 24. No interim analysis is planned. All withdrawn patients will be monitored at a reduced follow-up schedule.

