### Figure 4-1. Treatment Scheme

\*: Biopsy    tt: Target Trough level  
LD: 0.1 mg/kg/day    SOC: Standard of Care

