### **Arms 1 and 2 (Everolimus Groups)**

Initial dosing of ERL will be 1 tablet of 0.75 mg ERL BID (1.5 mg/day) for patients randomized into either one of ERL groups. Additional medication for dose adjustments will be provided in 0.5 mg or 0.75 mg tablet strengths. The investigator is responsible for instructing the patients regarding the exact dose and dosing schedule to be followed. At Day 7, ERL will be dosed to target trough levels of 3 to 8 ng/ml. At Month 3, ERL will be dosed to target levels of 5 to 8 ng/mL. The ERL trough level should remain less than 8 ng/mL during the whole study duration.

Patients may require dose adjustments based on tolerability, individual response, changes in co-medications, or clinical condition. Dose adjustments can be made at 4-5 day intervals.

Everolimus and tacrolimus should be taken at the same time and consistently either before, during or after meals.

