## **On Day 7 after initiation of Everolimus treatment**

For Arm 1 and Arm 2 (ERL groups), the 0.75 mg BID dose will be increased if the ERL trough level is < 3 ng/mL, and reduced if the ERL trough level is > 8 ng/mL until Month 3. Starting at Month 3, ERL will be dosed to target levels of 5 to 8 ng/mL. The dose will be increased if the ERL trough level is < 5 ng/mL, and reduced if the ERL trough level is > 8 ng/mL.

Everolimus dose adjustments should be made on results of the trough levels from the hospital laboratory. Tacrolimus dose adjustments should be made based on the results of the trough levels done at the local laboratory. Tacrolimus trough levels will also be run at the hospital laboratory for purposes of the protocol.

Follow-up ERL and TAC trough levels should be measured 5-7 days after any dose adjustment to ERL or TAC to ensure that the recommended troughs are achieved.

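### From Month 3, Section 6.5.5 requires an everolimus dose increase below 5 ng/mL, but the synopsis trigger and the Section 7.5.6 alert stay at 3 ng/mL

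*Combined protocol and SAP*

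**What the plan says.** The two sections that govern prescribing and dose adjustment agree with each other. Section 6.5.4, for Arms 1 and 2, states: "At Month 3, ERL will be dosed to target levels of 5 to 8 ng/mL". Section 6.5.5 applies the limits of 3 and 8 ng/mL only for the first period, with the dose "reduced if the ERL trough level is > 8 ng/mL until Month 3". It then sets 5-8 ng/mL and adds: "The dose will be increased if the ERL trough level is < 5 ng/mL".

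The synopsis does not carry this step. For Arm 1 it says: "From Day 5 on, the everolimus 0.75 mg BID dose will be increased if the trough level is < 3 ng/mL". The Arm 2 paragraph uses the same words. Neither gives an end date or a later everolimus limit, although both give a Month 3 change for tacrolimus.

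Section 7.5.6 makes drug monitoring mandatory for the whole study and then sets the alert: "The transplant team will be alerted when ERL trough levels are < 3 ng/mL or > 8 ng/mL". It gives the purpose of the alert as adjusting the everolimus dose, and it contains no Month 3 step.

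The Section 4 text says: "Everolimus will be dosed to target trough levels of 3 to 8 ng/ml, starting on Day 7". It is silent on Month 3. Figure 4-1 is not shown in the text available for this review, but its legend includes "tt: Target Trough level", so the figure may show a later everolimus target.

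**The concern.** The plan describes everolimus as concentration-controlled, so the trough target is part of the definition of the treatment. From Month 3 the plan gives two different lower limits for acting on the trough. Two patients with the same result could be dosed differently while each is treated according to a written instruction.

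The timing makes this more than an editorial matter. At Month 3 the Arm 1 tacrolimus target falls from 4-7 to 2-5 ng/mL. Arm 2 stops tacrolimus altogether: "Patients on Arm 2 will be converted between weeks 12 and 14, after the protocol biopsy". The everolimus target becomes uncertain just when the companion drug is lowered or removed, and it stays uncertain for the remaining 21 of 24 months.

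There is also a consequence for analysis. Section 10.1 excludes patients with a major protocol violation or deviation from the Per Protocol Set. The documents do not settle whether leaving the dose unchanged at 4 ng/mL after Month 3 is a deviation at all.

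**Working it through.** **Step 1: compare the rules from Month 3 onward.**

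| Trough (ng/mL) | 6.5.5 | Synopsis, Arms 1 and 2 | 7.5.6 alert |
|---|---|---|---|
| below 3 | increase | increase | yes |
| 3 to <5 | increase | no increase called for | no |
| 5 to 8 | no change | no change | no |
| above 8 | reduce | reduce | yes |

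The upper limit of 8 ng/mL agrees everywhere. Only the band from 3 to just under 5 ng/mL differs. Before Month 3 the limits in 6.5.5, the synopsis and 7.5.6 are the same.

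**Step 2: count the scheduled troughs subject to the rule.** The plan states no such figure, so there is nothing to reproduce.

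- Visits from Month 3 in Table 7-1: Months 3, 4, 6, 8, 10, 12, 15, 18, 21 and 24, which is 10.
- Section 6.5.9 provides no drug after Month 24, so that trough cannot lead to a study dose change: 10 - 1 = 9.
- Section 6.3 plans 16 patients per arm: 16 × 9 = 144 per everolimus arm and 2 × 144 = 288 for both, before attrition.
- In Arm 2 the Month 3 trough may precede conversion. Without it the count is 16 × 8 = 128.

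**Step 3: see how firm the count is.** Section 4 says fifty patients will be randomized. Fifty over three arms averages 50 / 3 = 16.7, and an arm of 17 gives 17 × 9 = 153. Section 6.5.5 also asks for a repeat trough 5-7 days after any dose change, and these repeats are not counted. Attrition works the other way. The figure of 144 is therefore an order of size, not an upper bound.

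**Step 4: the share in the band.** The documents give no distribution of everolimus troughs, so the fraction between 3 and <5 ng/mL cannot be derived. They also give no rejection risk for 3 to <5 against 5-8 ng/mL.

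**The case against.** The strongest reply is that the sections a clinician would dose from are clear. Sections 6.5.4 and 6.5.5 agree, and 6.5.5 states the 5 ng/mL trigger outright. On this view the synopsis is a summary that was not updated, and the alert is only a prompt that can run alongside a stricter dosing rule. Much of this stands: the body does not contain two rival dosing regimens. It does not remove the point, because no precedence rule is written and Section 7.5.6 is itself body text. Its alert exists to adjust the everolimus dose, yet it omits a band in which 6.5.5 requires an adjustment.

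A reader might infer more than the documents support:

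- **That low troughs go unnoticed, or that a missing alert leaves a trough of 4 ng/mL untreated.** Monitoring is mandatory and the scheduled result is visible. A clinician following 6.5.5 would still raise the dose. The fault lies in the conflicting thresholds.
- **That exposure will differ.** It will only if staff dose from the synopsis or wait for an alert.
- **That Section 4 also contradicts 6.5.5.** Its text is silent on Month 3, and Figure 4-1 may show the step.

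**Conclusion.** The point holds as an inconsistency in operative dosing text. From Month 3, a trough of 3 to <5 ng/mL requires an increase under 6.5.5, requires none under the synopsis, and raises no alert under 7.5.6. This could alter everolimus exposure in both investigational arms. With 16 patients per arm, the rule covers about 144 scheduled troughs per everolimus arm (Months 3 to 21), and somewhat more if fifty patients are randomized. That number counts the occasions on which the rule applies, not the troughs in dispute. A reader might go on to infer a higher rejection rate, but the documents give no basis for sizing or asserting one.

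The threshold conflict rests on the text alone and needs no assumption. The count assumes the Table 7-1 visits, the planned arm size and no attrition. The point should be fixed: it concerns a decision threshold, and the correction is small.

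**What to change.** If the Month 3 step is intended, as 6.5.4 and 6.5.5 indicate:

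- Set the Section 7.5.6 alert to <3 or >8 ng/mL until Month 3, and to <5 or >8 ng/mL from Month 3.
- State the same step in the synopsis paragraphs for Arms 1 and 2.
- Align the Section 4 sentence if Figure 4-1 does not already show the step.

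If 3-8 ng/mL throughout is intended, correct 6.5.4 and 6.5.5 instead.

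The 3-8 ng/mL range in Section 6.5.7.5 can stay, since it decides whether a patient treated for BK virus remains in the study. If such patients may be held at 3 to <5 ng/mL after Month 3, mark this as an exception to the increase rule. The discontinuation limit in 6.5.8 needs no change.

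The cost is one laboratory alert setting and a few sentences of wording, made through a written amendment approved by the IRB as Section 12.1 requires. No change to sample size, visits or analysis is needed.
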